7.6. Treatment Compliance

For the purpose of compliance calculation, there will be three study intervals:

- Baseline Visit to Week 1
- Week 1 to Week 6
- Week 6 to Month 3

The compliance rate for a subject will be calculated as follows for each study interval:

$$\text{Compliance Rate (\%)} = (2 * \text{Duration} - \sum \text{Miss}) / (2 * \text{Duration}) \times 100$$

Where

Duration: The number of days subject should have administered study medication, calculated as:

Study Interval	Equation for Duration Calculation
Baseline Visit to Week 1	Week 1 Visit date – Date of first drug dispensation
Week 1 to Week 6	Week 6 Visit date – Week 1 Visit date
Week 6 to Month 3	Month 3 Visit date – Week 6 Visit date

Miss: The number of missed doses since the last visit.

For subjects in the FAS, the compliance rate will be summarized by post-baseline study interval by planned treatment.

7.7. Exposure to Study Medication

The duration of exposure to a study medication is measured by days on treatment as derived in [Section 4.1.6](#). For subjects in the Safety Population, the duration of exposure will be summarized using descriptive statistics, and frequency and percentage of subjects will be tabulated by duration category (1-30 days, 31-60 days, or ≥ 61 days) by actual treatment received.

8. EFFICACY ANALYSES

Unless specified otherwise, efficacy analyses will be performed on the study eye, based on the FAS, and summarized by planned treatment, irrespective of the actual treatment received.

Unless otherwise specified, for subjects who receive IOP-lowering rescue therapy, any IOP values collected after the receipt of rescue therapy will be censored (i.e., treated as missing) in the analyses.

8.1. Analyses of Primary Endpoint and Key Secondary Endpoints

8.1.1. Primary Analyses

8.1.1.1. Primary Endpoint

The primary efficacy endpoint is IOP in the study eye at each scheduled timepoint (08:00, 10:00, and 16:00) at each of three follow-up visits, Week 1, Week 6, and Month 3. The nine combinations of three scheduled timepoints at each of three follow-up visits are referred to subsequently as nine timepoints. For the primary endpoint, the following null (versus alternative) hypothesis will be tested:

$$H_0: \mu_T - \mu_C > \Delta, \text{ for at least one timepoint}$$

versus

$$H_A: \mu_T - \mu_C \leq \Delta \text{ at all nine timepoints}$$

where μ_T and μ_C denote the mean values of the primary endpoint in the DE-117 arm and the Timolol arm, respectively, and Δ denotes the non-inferiority margin of 1.5 mmHg or 1.0 mmHg as specified below.

The primary analysis of the primary efficacy endpoint will be performed using a MMRM of IOP based on the FAS. A separate MMRM will be used for IOP at each scheduled timepoint (8:00, 10:00, or 16:00). For each scheduled timepoint, the model will include treatment (T_i), analysis visit (V_j), and treatment-by-visit interaction (TV_{ij}) as fixed effects, and baseline IOP at the scheduled timepoint as a covariate. Correlations of IOP measurements within-subject will be modeled using an unstructured covariance matrix. The mathematical model is given by:

$$IOP_{ijn} = \mu + T_i + V_j + TV_{ij} + \varepsilon_{ijn}$$

where μ denotes the overall mean, and ε denotes the random error associated with the individual subject. The above model allows treatment effect and its variability to vary over study visits.

If there are convergence issues, covariance matrix structures other than unstructured will be tried in the following order: (1) heterogeneous Toeplitz (TOEPH), (2) heterogeneous autoregressive of order 1 (ARH(1)), (3) heterogeneous compound symmetry (CSH), and (4) compound symmetry (CS). The first covariance structure that converges will be used as the primary analysis. Least squares mean IOP values for each treatment arm and differences between least squares treatment arm means and associated 95% confidence intervals will be reported for each of the nine timepoints.

Non-inferiority criteria for primary endpoint: With respect to the primary study objective, non-inferiority of DE-117 to Timolol is achieved if the upper limit of the two-sided 95% confidence interval for the difference in the mean IOP (DE-117 minus Timolol) is ≤ 1.5 mmHg at all nine timepoints and ≤ 1.0 mmHg at a majority (five or more) of the nine timepoints.

Superiority of DE-117 to Timolol for the primary efficacy endpoint is achieved if the upper limit of the two-sided 95% confidence interval for the difference in the mean IOP (DE-117 minus Timolol) is < 0 mmHg at all nine timepoints.

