### 8.1. Subject Inclusion Criteria for ADULT Subjects

#### Inclusion Criteria Specific for ADULT Subjects:

At Visit 1 (Screening), the subjects must meet all of the following inclusion criteria:

1. Provide signed written informed consent on the Institutional Review Board (IRB)/Ethics Committee (EC) approved Informed Consent Form (ICF).
2. Be 18 years of age or older on the date of signing the ICF and be able and willing to comply with all treatment and follow-up study procedures.
3. If a subject is a female of childbearing potential (i.e., not post-menopausal [within 12 months since the last menses] or not surgically sterile [less than 6 months from date of surgery]), she must have a negative urine pregnancy test and must use at least one of the following acceptable contraceptive methods during the study (as well as for 4 weeks following last dose in study).
  - Abstinence
  - Hormonal contraceptive method (including oral or transdermal contraceptives, injectable progesterone, progestin subdermal implants, progesterone-releasing intrauterine devices [IUDs]) initiated at least 28 days prior
  - Placement of a copper-containing IUD
  - Condom with spermicidal foam/gel/film/cream/suppository
  - Vasectomized male partner (surgery at least 6 months prior)

Male subjects capable of fathering children should use/ practice an acceptable contraceptive method, such as abstinence, condom or vasectomy (surgery at least 6 months prior) or other contraceptive method deemed adequate by the investigator throughout the course of the study (as well as for 12 weeks following last dose in study).

4. Must have a diagnosis of OAG (including Pigmentary Glaucoma or Pseudoexfoliative Glaucoma) or OHT in both eyes, or one eye with OAG and the other with OHT.
5. BCVA of +0.60 logMAR (Snellen equivalent 20/80) or better in each eye.
6. Central corneal thickness  $\geq 480 \mu\text{m}$  and  $\leq 600 \mu\text{m}$  in each eye.
7. Anterior chamber angle grade  $\geq 2$  (Shaffer scale) in each eye.

In addition to continuing to meet inclusion criterion 5 (BCVA), the subject must meet the following criteria at Visit 2 (Baseline, Day 1):

8. Completed the required wait/washout period.

9. At all time points of IOP measurements (08:00, 10:00 and 16:00) at Visit 2 (Baseline, Day 1), have IOP of  $\geq 22$  mmHg in at least one eye (the same eye), and  $\leq 34$  mmHg in both eyes.

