3.2. Randomization and Masking

A blocked randomization stratified by age (< 18 and ≥ 18 years old) will be employed to randomize eligible subjects in a 1:1 ratio to receive either DE-117 or Timolol. The randomization schedule will be generated and implemented by an independent CRO, Medidata Solutions, Inc. (New York City, NY).

This is a double-masked study. The subjects, Investigators, Examiners, and Santen personnel involved in the conduct of the study will be masked to the study treatment. An authorized unmasked study staff member who is not the Investigator or Examiner at the investigative site

will dispense and collect study medication(s) and will query about dosing compliance. In case of a medical emergency, when the unmasking of a subject's treatment assignment code becomes necessary for the welfare of that subject, the Clinical Investigator may reveal the treatment information by unmasking which treatment the subject has received through the study's interactive web response system (Medidata RTSM).

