3.3. Sample Size Planning

The sample size calculation was based on a two-sided Type I error rate of 5% and a non-inferiority margin of 1.5 mmHg. Assuming a treatment difference of 0 mmHg between the DE-117 arm and the Timolol arm, a standard deviation (SD) of 4.0 mmHg, and a correlation coefficient of 0.6 among repeated measures, approximately 400 adult subjects in total (200 subjects per treatment arm) will provide 90% power to demonstrate non-inferiority of DE-117 Ophthalmic Solution 0.002% to Timolol Maleate Ophthalmic Solution 0.5% in IOP-lowering effect.

The standard deviation of 4.0 mmHg was determined from previous DE-117 studies conducted in the United States: 33-002 and 33-003.

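### The primary MMRMs adjust only for the time-matched baseline IOP; adding baseline mean diurnal IOP before unmasking may gain some precision and costs almost nothing

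*SAP*

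**What the plan says.** SAP 8.1.1.1 specifies a separate MMRM for 08:00, 10:00 and 16:00. Each has treatment, analysis visit and treatment-by-visit interaction "as fixed effects, and baseline IOP at the scheduled timepoint as a covariate", with unstructured within-subject covariance. The equation printed below that sentence has no baseline term. SAP 8.1.1.2.2 reuses the same model in study eyes with baseline mean diurnal IOP below 25 mmHg. For mean diurnal IOP, SAP 8.1.1.2.1 adjusts for baseline mean diurnal IOP, so the three readings are already pooled there.

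Non-inferiority requires the upper 95% limit to be "≤ 1.5 mmHg at all nine timepoints and ≤ 1.0 mmHg at a majority (five or more) of the nine timepoints".

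Adult inclusion criterion 9 (Protocol 8.1) opens with "At all time points of IOP measurements (08:00, 10:00 and 16:00) at Visit 2 (Baseline, Day 1" and goes on to require at least 22 mmHg in the same eye and no more than 34 mmHg in both eyes. Protocol 7.4.3 places randomization after the 16:00 reading. SAP 3.1 records that no pediatric subject was randomized.

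SAP 3.3 bases the sample size on a "two-sided Type I error rate of 5% and a non-inferiority margin of 1.5 mmHg", a true difference of 0, and "a standard deviation (SD) of 4.0 mmHg, and a correlation coefficient of 0.6 among repeated measures". It states that "approximately 400 adult subjects in total (200 subjects per treatment arm) will provide 90% power to demonstrate non-inferiority".

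**The concern.** A single IOP reading is a noisy measure of a subject's untreated level. If the other two baseline readings predict follow-up IOP beyond what the time-matched reading tells, leaving them out leaves explainable variance in the residual and widens the intervals. That matters here because all nine upper limits must meet 1.5 mmHg and at least five must meet 1.0 mmHg, while the sample-size text names only the 1.5 margin. The 1.0 limit has little slack: at SD 4.0 and 200 per arm, one timepoint meets it with about 70% probability. The readings are already in hand, so any gain needs no new data.

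**Working it through.** **Inputs.** From SAP 3.2 and 3.3: 200 per arm, 1:1, difference 0, SD 4.0, correlation 0.6, two-sided 5%. From SAP 8.1.1.1: the two-part rule. From Protocol 8.1: entry limits of 22 to 34 mmHg. Assumed, because the documents do not give them: every correlation involving a baseline reading, and the untreated mean and SD behind the entry limits.

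**1. The plan's 90%.** SE = 4.0 × √(2/200) = 0.40 mmHg.
- One timepoint, limit 1.5: Φ(1.5/0.40 − 1.96) = Φ(1.79) = 96.3%.
- One timepoint, limit 1.0: Φ(1.0/0.40 − 1.96) = Φ(0.54) = 70.5%.
- Nine unadjusted timepoints, correlation 0.6 (simulated): 83.7% for 1.5 at all nine, 72.3% for the full rule.
- Three other calculations come within 2 points of 90%: change scores, 1.5 at all nine (90.2%); Month 3 timepoints only, unadjusted, 1.5 (91.6%); one-baseline adjustment with residual SD 3.20 and residual correlation 0.6, full rule (92.0%).

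The 90% can be reached, but the documents do not say which calculation gave it, or whether SD 4.0 is before or after baseline adjustment.

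**2. Best case: 0.6 for every pair, no entry limits, SD 4.0 unadjusted.**
- One baseline: residual variance 1 − 0.6² = 0.640; residual SD 4.0 × √0.640 = 3.20.
- Three baselines: R² = 3 × 0.36/(1 + 2 × 0.6) = 0.491; residual variance 0.509; residual SD 2.85. When the other two readings predict equally well, time-matched baseline plus baseline mean diurnal IOP gives the same result.
- Half-width = 1.96 × SD × √(2/200): 0.627 falls to 0.559 mmHg. The ratio is √(0.509/0.640) = 0.892, so intervals are 10.8% narrower.
- Residual correlations under the planned models: (0.6 − 0.72 + 0.36)/0.64 = 0.375 within a clock time, but (0.6 − 0.36 − 0.36 + 0.216)/0.64 = 0.15 between clock times, because each model has a different covariate. With all three baselines the correlation is (0.6 − 0.491)/0.509 = 0.214 throughout.
- Full-rule power by simulation of nine correlated differences: 95.6% rises to 99.2%.

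**3. Other correlations, no entry limits** (follow-up correlation 0.6 throughout).

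| Baseline–baseline / same-time / cross-time | Width ratio | Full-rule power |
|---|---|---|
| 0.5 / 0.5 / 0.5 | 0.913 | 88.4% to 95.0% |
| 0.6 / 0.5 / 0.5 | 0.937 | 88.2% to 93.1% |
| 0.8 / 0.6 / 0.6 | 0.956 | 94.8% to 96.8% |
| 0.6 / 0.4 / 0.4 | 0.965 | 82.0% to 85.5% |
| 0.7 / 0.6 / 0.5 | 0.986 | 94.1% to 94.7% |
| 0.8 / 0.6 / 0.5 | 0.999 | 93.7% to 93.7% |

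The gain is exactly zero when the cross-time correlation equals same-time × baseline–baseline, for example 0.48 = 0.6 × 0.8.

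**4. With the entry limits** (all three readings within 22 to 34; assumed untreated mean 25, SD 4). Width ratios are about 0.93 for 0.6/0.6/0.6, 0.967 for 0.8/0.6/0.6, 0.991 for 0.7/0.6/0.5 and 0.999 for 0.8/0.6/0.5. The gain shrinks because selecting on all three readings has already used part of their information. At assumed means of 24 and 26 with 0.6 for all pairs, the one-baseline residual SD is 3.05 and 3.07, against 3.20 without limits, while the three-baseline value stays near 2.85.

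**5. Subgroup below 25 mmHg.** Each reading is at least 22 and their mean is below 25, so baseline hardly varies. Intervals are 0 to 1.2% narrower.

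**The case against.** The strongest reply is that nothing here is wrong. Adjusting IOP at a clock time for baseline IOP at that time is valid, leaves Type I error unaffected, and delivers the baseline adjustment promised in SAP 6.1. This stands in full: the point concerns efficiency, not bias.

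A reader might infer that all nine intervals are certainly wider than necessary, by about 11%, on the plan's own assumption. The documents do not support that. SAP 3.3 gives 0.6 for repeated measures without saying that it covers baseline-to-follow-up or cross-clock-time pairs. In a model fitted per clock time, the repeated measures are the three post-baseline visits. The 10.8% also ignores the entry limits.

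A reader might also infer from the printed equation that baseline is left out of the model. The sentence before it names the covariate, so this is notation. The Appendix A code is not in the supplied text and could not be checked.

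It can also be said that not every analyzed subject need have three readings, since the FAS (SAP 5.3) accepts baseline IOP at any timepoint. That is correct as wording. Given criterion 9, it should matter only for protocol deviations, and SAP 4.2.2 already has a rule for a missing baseline.

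**Conclusion.** The concern holds as an optional gain in precision. The primary models leave out two baseline readings that entry requires, and using them should not widen the intervals in expectation, because one more covariate costs almost nothing with about 400 subjects. A realistic range under the entry limits is 0 to 7% narrower, given an assumed untreated mean of 25 and SD of 4. The upper end needs the other clock times to predict as well as the time-matched one. The 10.8%, and the rise in power from 95.6% to 99.2%, are a best case that rests on 0.6 for all pairs, SD 4.0 as the unadjusted SD, and no entry limits. For the SAP 8.1.1.2.2 subgroup the gain is negligible. No gain was shown for letting the baseline slope vary by visit.

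**What to change.** Before unmasking, in SAP 8.1.1.1:

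- Add baseline mean diurnal IOP as a second covariate next to the time-matched baseline IOP. SAP 8.1.1.2.2 inherits the change because it reuses the model.
- State that the SAP 4.2.2 rule applies to any missing baseline reading, so that the mean diurnal covariate is defined for every FAS subject.
- Show the baseline terms in the printed equation and make the Appendix A code match.
- Treat baseline-by-visit terms as optional.

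The cost is a sentence, an equation and one extra parameter per model. No new data or derived variable is needed.

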8.1.1.2. Key Secondary Endpoints

8.1.1.2.1. Mean Diurnal IOP at Month 3

The first key secondary endpoint is mean diurnal IOP in the study eye at Month 3. The following null (versus alternative) hypothesis will be tested:

$$H_{0SI}: \mu_{TI} - \mu_{CI} \geq \Delta \text{ versus } H_{ASI}: \mu_{TI} - \mu_{CI} \leq \Delta$$

where μ_{TI} and μ_{CI} denote the mean diurnal IOP at Month 3 in the DE-117 and Timolol arm, respectively, and Δ denotes the non-inferiority margin of 1.5 mmHg. The primary analysis of this key secondary efficacy endpoint will be performed using a MMRM based on the FAS. The model will include treatment, analysis visit (Week 1, Week 6, or Month 3), and treatment-by-visit interaction as fixed effects, and baseline mean diurnal IOP as a covariate. Correlations of mean diurnal IOPs within-subject will be modeled using an unstructured covariance matrix. The mathematical model is analogous to the model in the primary efficacy endpoint.

If there are convergence issues, covariance matrix structures other than unstructured will be tried in the following order: (1) heterogeneous Toeplitz (TOEPH), (2) heterogeneous autoregressive of order 1 (ARH(1)), (3) heterogeneous compound symmetry (CSH), and (4) compound symmetry (CS). The first covariance structure that converges will be used as the primary analysis. Least squares mean diurnal IOP values at Month 3 for each treatment arm and the difference between least squares treatment group means and its 95% confidence interval will be reported.

Non-inferiority of DE-117 to Timolol is achieved for this endpoint if the upper limit of the 95% confidence interval for the difference between DE-117 and Timolol (DE-117 minus Timolol) in the mean diurnal IOP at Month 3 is ≤ 1.5 mmHg. Superiority of DE-117 to Timolol is achieved for this endpoint if the upper limit of the 95% confidence interval is < 0 mmHg.

8.1.1.2.2. IOP at Nine Timepoints in Study Eyes with Baseline Mean Diurnal IOP < 25 mmHg

The second key secondary endpoint is IOP at each scheduled timepoint (08:00, 10:00, and 16:00) at each of three follow-up visits, Week 1, Week 6, and Month 3, in the study eyes with mean diurnal IOP < 25 mmHg at the Baseline Visit. If non-inferiority of DE-117 to Timolol for the primary endpoint and the first key secondary endpoint is achieved, the following null (versus alternative) hypothesis will be tested for the second key secondary endpoint:

$$H_{0S2}: \mu_{T2} - \mu_{C2} > \Delta, \text{ for at least one timepoint}$$

versus

$$H_{AS2}: \mu_{T2} - \mu_{C2} \leq \Delta \text{ at all nine timepoints}$$

where μ_{T2} and μ_{C2} denote the mean IOP values in the DE-117 arm and the Timolol arm, respectively, and Δ denotes the non-inferiority margin of 1.5 mmHg or 1.0 mmHg as specified below.

The same MMRM used in the analysis of the primary efficacy endpoint will be used for the analysis of the second key secondary endpoint. Non-inferiority of DE-117 to Timolol for this endpoint (i.e., for subjects with baseline mean diurnal IOP < 25 mmHg) is achieved if the upper limit of the two-sided 95% confidence interval for the difference in the mean IOP (DE-117 minus Timolol) is ≤ 1.5 mmHg at all nine timepoints and ≤ 1.0 mmHg at a majority (five or more) of the nine timepoints. Superiority of DE-117 to Timolol for this endpoint (i.e., for subjects with baseline mean diurnal IOP < 25 mmHg) is achieved if the upper limit of the two-sided 95% confidence interval for the difference in the mean IOP (DE-117 minus Timolol) is < 0 mmHg at all nine timepoints.

8.1.1.2.3. Mean Diurnal IOP at Week 1

The third key secondary endpoint is mean diurnal IOP in the study eye at Week 1. If non-inferiority of DE-117 to Timolol for the primary and the first two key secondary endpoints is achieved, then the following null (versus alternative) hypothesis will be tested for the third key secondary endpoint:

$$H_{0S3}: \mu_{T3} = \mu_{C3} \text{ versus } H_{AS3}: \mu_{T3} \neq \mu_{C3}$$

where μ_{T3} and μ_{C3} denote the mean diurnal IOP at Week 1 in the DE-117 and Timolol arm, respectively. The primary analysis of this key secondary endpoint will be performed using a MMRM analogous to the model used for the first key secondary efficacy endpoint (mean diurnal IOP at Month 3).

For the primary and key secondary efficacy endpoints, the testing sequence and multiplicity adjustment details are provided in [Section 6.4](#).

8.1.2. Sensitivity Analyses

For the primary endpoint and the key secondary endpoints, sensitivity analyses will be performed to assess the robustness of the results from the primary analysis. The sensitivity analyses consist of two types: (1) assessment based on the PPS and (2) a pattern-mixture model (PMM) approach ([Table 6](#)). Unless otherwise specified, for subjects who receive IOP-lowering rescue therapy, any IOP values collected after the receipt of rescue therapy will be censored (i.e., treated as missing) in the analyses.

Table 6: Overview of Primary and Sensitivity Analysis Methods

Primary or Sensitivity Analysis	Statistical Method	Analysis Population	Handling of Missing Data
Primary Analysis	MMRM	FAS	Observed cases
Sensitivity Analyses	MMRM	PPS	Observed cases
	PMM with delta-adjustment	FAS	MI

Abbreviations: FAS = full analysis set; MI = multiple imputation; MMRM = mixed-effects model for repeated measures; PMM = pattern-mixture model; PPS = per protocol set.

To assess the sensitivity to departure from MAR assumption, a PMM with delta-adjustment will be applied, as follows:

- a. Use Markov chain Monte Carlo (MCMC) to create monotone missingness first. Then obtain standard multiple imputations under MAR assumptions for missing IOP values using monotone regression. The missing data are filled in and 50 complete datasets are created. The seed that will be used in the SAS program is 13546.
- b. For each IOP value that had been missing because of (1) censoring after having received IOP-lowering rescue therapy; or because of (2) early study discontinuation due to lack of efficacy or AE, regardless of treatment arm, adjust these values by adding delta to the imputed values, where delta = 1.0 mmHg. The seed that will be used in the SAS program is 13546.
- c. Each of the 50 complete datasets will then be analyzed separately using the same MMRM as used for the primary analysis.
- d. The estimates obtained from the MMRM analysis of each complete dataset are combined for inference purposes.
- e. Repeat step b, c, d, with delta = 2.0, 3.0, 4.0, and 5.0 mmHg. The larger the value of delta that is required to reverse the conclusion of the primary analysis, the more robust the conclusion is considered to be.

The main part of the SAS code for the specified MMRM analysis and PMM are provided in Appendix A ([Section 12.1](#)) and Appendix B ([Section 12.2](#)), respectively.

For the primary endpoint, in addition to the two types of sensitivity analyses described above, if the overall rate of study drug discontinuation due to lack of efficacy or AE is greater than 10% and the difference between the rate in the DE-117 and Timolol arms is greater than 5 percentage points, a trimmed mean analysis ([Permutt et al., 2017](#)) will be conducted as a sensitivity analysis.

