5. STUDY POPULATION

5.1. Intent-to-Treat Population

The *Intent-to-Treat* (ITT) population will include all randomized subjects.

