5.3. Full Analysis Set

The Full Analysis Set (FAS) will include all randomized subjects who received at least one dose of study medication and provided Baseline IOP data (at any timepoint) and at least one post-baseline IOP measurement (at any timepoint). Efficacy analyses will be performed using the FAS and summarized by treatment as randomized.

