10. ADDITIONS AND CHANGES TO THE PROTOCOL-SPECIFIED ANALYSES

10.1. Full Analysis Set Definition

The full analysis set definition has been updated to add the requirement that baseline IOP data has to be present:

The Full Analysis Set (FAS) will include all randomized subjects who received at least one dose of study medication and provided Baseline IOP data (at any timepoint) and at least one post-baseline IOP measurement (at any timepoint). Efficacy analyses will be performed using the FAS and summarized by treatment as randomized.

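### The delta-adjusted PMM and the conditional trimmed mean run on the FAS, so treated subjects with no post-baseline IOP at all are never imputed or penalised, and the tipping point can overstate robustness.

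*SAP*

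**What the plan says.** SAP 5.3 admits a randomised, treated subject to the FAS only if the subject "provided Baseline IOP data (at any timepoint) and at least one post-baseline IOP measurement (at any timepoint"). SAP 10.1 repeats this as a change from the protocol; the change adds the baseline requirement.

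SAP 8.1.2 describes the main stress test: "To assess the sensitivity to departure from MAR assumption, a PMM with delta-adjustment will be applied". The row of Table 6 reads "PMM with delta-adjustment FAS MI". Step b adds delta (1.0 mmHg, then 2.0 to 5.0 in step e) to imputed values that were missing after rescue, or because the subject left the study for lack of efficacy or an adverse event.

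For the primary endpoint only, a trimmed mean is added if "the overall rate of study drug discontinuation due to lack of efficacy or AE is greater than 10" percent and the arms differ by more than 5 percentage points. That paragraph names no population, so the general rule of SAP Section 8 applies: "Unless specified otherwise, efficacy analyses will be performed on the study eye, based on the FAS".

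The remaining sensitivity analysis uses the Per-Protocol Set, a subset of the FAS (SAP 5.4). SAP 5.1 defines an Intent-to-Treat group that "population will include all randomized subjects", but it is used for disposition (SAP 7.1) and for no efficacy analysis. Protocol 14.4.2 confines efficacy analysis to the FAS or a subset of it.

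**The concern.** Step b is there to penalise values lost because a subject left for an adverse event or lack of efficacy. The population rule removes the subjects for whom every post-baseline value is lost for that reason. They enter no efficacy analysis.

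This matters because SAP 10.3 drops LOCF on the ground that the PMM is enough to judge robustness. The PMM is then the only analysis departing from missing-at-random that always runs, since the trimmed mean needs both triggers. Step e measures robustness by the delta needed to overturn the primary conclusion. If exits without any IOP reading are more common on DE-117, that delta comes out too large, in favour of non-inferiority.

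**Working it through.** **Who is left out.**
- Protocol 8.5 asks for the early-termination procedures, IOP included, on the day the drug is stopped, as far as possible. It also encourages continued visits.
- An IOP taken on Days 2 to 22 maps to Week 1 (SAP Table 2). That subject is in the FAS. If the subject left the study for an adverse event or lack of efficacy, the missing Week 6 and Month 3 values receive delta.
- SAP 5.3 asks for a measurement, not an uncensored one. A subject whose only post-baseline IOPs follow rescue therefore appears to be in the FAS and receives delta through the rescue part of step b.
- What remains is the treated subject with baseline IOP and no reading after it. The protocol's own example of lack of efficacy is an IOP above 34 mmHg after randomisation, which itself requires a reading. The gap is therefore mainly adverse-event exits before Week 1 with no exit measurement.

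**Size of the missed shift.** The plan gives no figure for this and no dropout rate. Let pT and pC be the shares of the DE-117 and timolol arms with no post-baseline IOP. Assume that all of them qualify for delta and that imputation from baseline and arm does not itself move the treatment difference. Then, at each of the nine timepoints:

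shift = delta × (pT − pC)

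| Assumed excess on DE-117, of 200 | delta 1 | delta 3 | delta 5 |
|---|---|---|---|
| 1 (0.5%) | 0.005 | 0.015 | 0.025 |
| 2 (1%) | 0.01 | 0.03 | 0.05 |
| 4 (2%) | 0.02 | 0.06 | 0.10 |
| 6 (3%) | 0.03 | 0.09 | 0.15 |
| 10 (5%) | 0.05 | 0.15 | 0.25 |

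(mmHg.) With 3% against 0.5% (6 against 1 of 200), the shift at delta 5 is 5 × 0.025 = 0.125 mmHg. With the FAS restriction these subjects contribute 0.

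**Room against the margins.** SAP 3.3 gives SD 4.0 mmHg, 200 per arm and a true difference of 0.
- SE = 4.0 × √(2/200) = 0.40.
- Upper limit at an observed difference of 0 = 1.96 × 0.40 = 0.784.
- Room below 1.0: 0.216. Room below 1.5: 0.716.
- Excess that uses up the room at delta 5: 0.216/5 = 4.3% and 0.716/5 = 14.3%. At delta 3: 7.2% and 23.9%.
- The 0.125 mmHg example gives 0.784 + 0.125 = 0.909, still below 1.0.

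**Effect on the two-part rule** (all nine upper limits ≤ 1.5, at least five ≤ 1.0), by simulation with nine equally correlated differences, 200 per arm and true difference 0:

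| Setting | shift 0 | shift 0.125 |
|---|---|---|
| SD 4.0, correlation 0.6 (SAP 3.3) | 72.2% | 58.4% |
| SD 3.2, correlation 0.375 (assumed) | 94.1% | 84.5% |

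The second row assumes that baseline correlates 0.6 with later values: 4.0 × √(1 − 0.36) = 3.2 and (0.6 − 0.36)/0.64 = 0.375. In the first row one excess subject at delta 5 gives 69.7%, and four give 61.3%. These are pass rates of a sensitivity run. Whether the SAP's 90% power refers to this rule is a separate question.

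**The case against.** The strongest reply is that the group is small and visible. Exit measurements keep many early leavers in the FAS, and lack-of-efficacy exits will nearly always have a reading. SAP 7.1 already reports how many randomised subjects are in the FAS by arm, and discontinuations by reason. The trimmed mean is conditional and covers the primary endpoint only. The protocol itself limits efficacy analysis to the FAS. All of this stands. It bounds the point but does not remove it, because a count in a disposition table does not enter the tipping point.

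Three stronger readings are tempting, and the documents do not support them.

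- A reader might infer that all the earliest dropouts escape the stress test. Those with an exit IOP do not; their later missing values receive delta when the reason qualifies.
- A reader might infer that Week 1 is left untested because of the FAS rule. Delta touches few Week 1 values mostly because an exit IOP on Days 2 to 22 counts as an observed Week 1 value, and observed values need no delta. Values censored after rescue still receive delta at Week 1.
- A reader might take the fall from 72% to 58%, or from 94% to 85%, as a loss in the chance of trial success. The primary MMRM is unchanged, because the omitted subjects have no outcome rows. The figures describe a sensitivity run at its largest delta under an assumed 2.5-point excess. SAP 8.1.2 also reads the PMM as a graded tipping point, not as pass or fail.

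**Conclusion.** The point holds in a limited form. The PMM by Table 6, and the trimmed mean by the Section 8 default, cannot reach treated subjects with baseline IOP and no post-baseline IOP, although step b is aimed at that kind of loss. The tipping point can overstate robustness if such exits are more common on DE-117.

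The size is unknown. It is negligible for one or two subjects or for balanced losses. It could change a reading of the 1.0 mmHg criterion at an excess of about 4.3% (9 of 200) at delta 5, given an observed difference of 0 and SE 0.40. That threshold assumes that delta has not already moved the difference through subjects in the FAS; if it has, against DE-117, less room is left. The direction is also an assumption, since the documents give no early-exit rates by arm. The primary result is not in question. This is a cheap improvement worth making.

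**What to change.** Before unmasking, amend Table 6 and SAP 8.1.2 as follows:
- Run the PMM, and the trimmed mean if triggered, on all randomised, treated subjects with baseline IOP.
- Impute subjects without post-baseline IOP from baseline and arm. Add delta when they left for an adverse event or lack of efficacy. In the trimmed mean, rank them among the worst outcomes.
- Keep the primary MMRM on the FAS.
- Record the departure from protocol 14.4.2 in SAP Section 10.
- Report FAS exclusions by arm and reason.

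The cost is SAP wording and a population flag in the imputation dataset. No new data are needed and the primary result does not change. The downside is that imputed values for a few subjects rest on baseline IOP alone. Randomised subjects who were never treated would still be left out.
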